5.2 Trial Treatments

The treatment to be used in this trial is outlined below in Tables 2 and 3

Table 2 Pembrolizumab Treatment

Drug	Dose/Potency	Dose Frequency	Route of Administration	Regimen/Treatment Period	Use
Pembrolizumab	200 mg	Every 3 weeks	IV infusion	6 three week cycles*	Experimental
The PEMBROLIZUMAB dosing interval may be increased due to toxicity as described in Section 5.2.1.2.					

Pembrolizumab should be administered 7 days (+/- 3 days) prior to the first fraction of hypofractionated radiation.

*NOTE: Patients who have stable or responding disease and are felt to be clinically benefiting from the drug can continue receiving pembrolizumab for up to 2 years. For cancers not currently commercially approved for treatment with pembrolizumab, the drug will be provided by Merck.

In the initial ***Safety Phase***, there will be two cohorts of patients based upon the radiotherapy dose delivered to the index metastatic lesion in the lung, liver, bone or soft tissue:

Cohort 1: 8 Gy x 3 to the index lesion

Cohort 2: 17 Gy x 1 to the index lesion*

*Subjects with locally advanced pancreatic cancer will be enrolled only in the 8 Gy x 3 cohort.

Patients are stratified by prior PD-1 therapy. 24 patients will be enrolled, 12 per stratum and 6 per fractionation cohort within each stratum. Standard safety decision-making will be used. The regimen is safe if no more than 0-1 dose-limiting toxicities (DLT) are observed in 6 patients within a cohort within a stratum. Enrollment in a cohort within a stratum will stop if 2+ DLT are observed within that cohort at any time during the safety phase. If 2+ DLT are observed in Cohort 1 in a stratum, then Cohort 2 within that stratum will still be tested. Cohort 1 → Cohort 2 is **not** an escalation of dose. DLT is defined as any Grade 3 or higher non-hematological toxicity and any Grade 4 hematological toxicity that is probably, possibly or definitely related to the combination of Pembrolizumab and hypofractionated radiotherapy.

Table 3. Hypofractionated Radiotherapy

Safety Phase:

Stratify	Progressed on Prior PD-1 (Melanoma or NSCLC) No Prior PD-1 (Pancreas, Breast or Other)	Cohort 1: 8 Gy x 3 → Cohort 2: 17 Gy x 1		TOTAL
		Number of Patients	Number of Patients	
		6	6	12
		6	6*	12
TOTAL		12	12	24
* Breast or Other cancer patients only				

Expansion Phase

Disease	Randomize		Number of Randomized Patients
	Cohort 1: 8 Gy x 3	Cohort 2: 17 Gy x 1	
Melanoma	7	7	14
NSCLC	7	7	14
Pancreas	6	0	6*
Breast	3	3	6

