Planning Target Volume (PTV) will be defined as per the convention for photon beam radiotherapy. A 3-dimensional margin will be created on the GTV or IGTV (if available) to allow for daily set-up variance.

Normal Structures

Organ at risk volume (OAR) is contoured as visualized on the planning CT or MR scan. Planning PAR is the OAR expanded for setup uncertainty or organ motion. The physician will contour the OAR. The dosimetrist will create the PAR by expanding the OAR by 2-3 mm, depending on the situation.

Dose Fractionation and Specification

The prescription dose per fraction to the PTV will be 8 Gy x three fraction for Cohort 1 and 17 Gy per fraction x one fractions in Cohort 2. The total dose for Cohort 2 will be 24 Gy over 3 fractions.

Treatment Planning

Three-dimensional coplanar or non-coplanar beam arrangements will be custom designed for each case to deliver highly conformal prescription dose distributions. Non-opposing, noncoplanar beams are preferable.

Many of the patients on this trial will undergo SBRT. For these patients, standard protocols and constraints that have been developed in the Department of Radiation Oncology will be followed. For SBRT, typically, ≥ 10 beams of radiation will be used with roughly equal weighting. Generally, more beams are used for larger lesion sizes. When static beams are used, a minimum of 7 non-opposing beams should be used. For arc rotation techniques, a minimum of 340 degrees (cumulative for all beams) should be utilized. For arc rotation techniques, a minimum of 340 degrees (cumulative for all beams) should be utilized. In order to obtain acceptable coverage, field aperture size and shape should correspond nearly identically to the projection of the PTV along a beam's eye view (i.e., no additional "margin" for dose buildup at the edges of the blocks or MLC jaws beyond the PTV). The only exception should be when observing the minimum field dimension of 3.5 cm when treating small lesions. As such, prescription lines covering the PTV will typically be the 60-90% line (where the maximum dose is 100%); however, higher isodoses (hotspots) must be manipulated to occur within the target and not in adjacent normal tissue.

Dose Selection/Modification

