5.8 Subject Replacement Strategy

Replacement of subjects will occur if the subject did not complete the course of therapy as defined as follows (unless they discontinue treatment because of a DLT).

Cohort 1: all 3 RT fractions and 3 of 6 Pembrolizumab doses, 1 before RT and 2 after RT

Cohort 2: 1 RT fraction and 3 of 6 Pembrolizumab doses, 1 before RT and 2 after RT

No subject can be replaced if they discontinue therapy as a result of DLT.

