6.0 TRIAL FLOW CHART

Table 8

	Main Study Screening Visit	Pembrolizumab Administration, Cycles 1-6	Hypofractionated Radiotherapy	Post-radiation Safety visit	Post-Pembrolizumab Safety visit	Post-treatment Follow up visit
Scheduling Window	-28 to -1	Days 1, 22, 43, 64, 85, 106 ± 3 Treatment completion = Day 106	Cohort 1: Day 8 ± 3 Cohort 2: Days 8, 10 & 12 ± 3	30 days ± 7 post completion of radiotherapy	30 days ± 7 post treatment completion (Day 136)	Day 196 ± 14
Informed consent	X					
Eligibility checklist review	X					
Tests and Observations						
History and PE	X	X – Days 1, 22, 43, 64, 85, 106 ± 3	X	X	X	X
ECOG score	X	X – Days 1, 22, 43, 64, 85, 106 ± 3	X	X	X	X
¹⁸ F-FDG PET/CT and/or CT scan or	X (also needed)					

May 3, 2017

Confidential  Limited Access

MRI – baseline@	for treatment planning study prior to Day 8)					
¹⁸ F-FDG PET/CT and/or CT scan or MRI – restaging **		X – Day 64			X	X
Biopsy or Archival Tissue***	X					X
CBC	X*	X – Days 1, 22, 43, 64, 85, 106 \pm 3			X	X
Comp Metabolic Panel	X*	X – Days 1, 22, 43, 64, 85, 106 \pm 3			X	X
Pregnancy Test*	X					
Toxicity Assessment	X	X	X	X	X	X
Correlative studies (Five 10 ml green top tubes and one	X ^a	X ^b – Days 1, 22, 43, 85 \pm 3	X – Day 8		X	X ^c

5 ml SST tube)						
----------------	--	--	--	--	--	--

X* - Measurements must be made within 21 days of signing study consent.

X@ - Imaging studies must be performed within 30 days \pm 3 of treatment initiation

** After radiological tumor assessment at screening, the first radiological assessment of tumor response status will be performed at day 64 (+/- 7 days), unless there is clinical indication warranting earlier radiologic imaging. If imaging at 64 days shows PD, treatment with pembrolizumab may continue until a repeat assessment 4-6 weeks later confirms PD. If this scan confirms progression of disease compared with previous scan that showed PD, then pembrolizumab should be discontinued.

Subsequent studies will be performed as per standard of care.

*** There is a potential for a second biopsy if patient is willing and has a lesion that is amenable.

^{a/b} The pre-treatment correlative studies sample can be drawn at either the main study screening visit or at Pembrolizumab infusion #1 (as long as the sample is drawn before the infusion takes place).

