7.0 TRIAL PROCEDURES

7.1 Trial Procedures

The Trial Flow Chart - Section 6.0 summarizes the trial procedures to be performed at each visit. Individual trial procedures are described in detail below. It may be necessary to perform these procedures at unscheduled time points if deemed clinically necessary by the investigator.

Furthermore, additional evaluations/testing may be deemed necessary by the Sponsor and/or Merck for reasons related to subject safety. In some cases, such evaluation/testing may be potentially sensitive in nature (e.g., HIV, Hepatitis C, etc.), and thus local regulations may require that additional informed consent be obtained from the subject. In these cases, such evaluations/testing will be performed in accordance with those regulations.

Study Visit Schedule

Days -28 to -1: Subject will be screened for enrollment in the study. After the subject is deemed potentially eligible for the study and consents, the subject will be seen in the outpatient radiation therapy and/or medical oncology clinics for a history, physical exam, baseline laboratory studies, correlative studies, scheduling of imaging studies (if needed), and scheduling of radiotherapy treatment planning and Pembrolizumab infusion. Radiotherapy treatment planning is a standard procedure and will consist of a simulation CT scan or ¹⁸F-FDG PET/CT or MRI scan as per the Department of Radiation Therapy standards. The simulation will be scheduled so that the subject may begin hypofractionated radiotherapy on Day 8 \pm 3

Day 1: Pembrolizumab infusion in medical oncology offices.

Day 8: Hypofractionated radiotherapy will be given in either three fractions of 8 Gy delivered on Days 8, 10 & 12 \pm 3 or, one fraction of 17 Gy delivered on day 8 \pm 3.

Days 1, 22, 43, 64, 85, 106 \pm 3: Pembrolizumab infusion in medical oncology offices. History, PE, ECOG assessment, correlative studies, and laboratory studies on Days 1, 22, 43, 64, 85, 106 \pm 3.

Day 38 or Day 42: Follow up safety visit with the radiation oncologist 30 days \pm 7 post completion of radiotherapy (Day 38 \pm 7 for Cohort 1 and Day 42 \pm 7 for Cohort 2). History, PE, and ECOG assessment.,

Day 106 \pm 7: Follow up safety visit with the radiation oncologist or medical oncologist 30 days \pm 7 post completion of the 6th cycle of Pembrolizumab. History, PE, ECOG assessment, laboratory studies, correlative studies, and imaging restaging will be performed at this visit.

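### Section 5.2, Table 8 and the Section 7.1 visit schedule attach the three-fraction regimen to Cohort 2, which is the single-fraction cohort

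*Combined protocol and SAP*

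**What the plan says.** The cohort definitions are consistent in most of the document. Section 2.1 and the cohort list in Section 5.2 give Cohort 1 three fractions of 8 Gy and Cohort 2 a single fraction: "Cohort 2: 17 Gy x 1 to the index lesion". Table 3, the per-fraction prescription sentence in Section 5.2 and Tables 11 to 13 in Section 8 agree. So does the replacement rule in Section 5.8, which requires "Cohort 1: all 3 RT fractions and 3 of 6 Pembrolizumab doses, 1 before RT and 2 after RT" and, for the other arm, "Cohort 2: 1 RT fraction and 3 of 6 Pembrolizumab doses".

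Three places say otherwise:

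1. **Section 5.2, Dose Fractionation and Specification.** Directly after the correct per-fraction sentence comes: "The total dose for Cohort 2 will be 24 Gy over 3 fractions". No total is given for Cohort 1.
2. **Section 6.0, Table 8, radiotherapy column header.** Cohort 1 has Day 8 only. The second entry reads "Cohort 2: Days 8, 10 & 12".
3. **Section 7.1, Study Visit Schedule, the Day 38 / Day 42 line.** The visit is placed at Day 38 plus or minus "7 for Cohort 1 and Day 42" plus or minus 7 for Cohort 2.

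The Day 8 line of the same schedule is correct but is written by regimen, without cohort numbers: "three fractions of 8 Gy delivered on Days 8, 10 & 12", or the single 17 Gy fraction on Day 8. The timing rule for the visit, in both Table 8 and Section 7.1, is 30 days plus or minus "7 post completion of radiotherapy".

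**The concern.** The affected places are a stated total dose, the treatment-day header of the flow chart and the days of a safety visit. Staff work from these directly, and Section 7.1.4 sends readers to the flow chart for visit requirements. Anyone following them by cohort number meets an instruction that contradicts Table 3.

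The radiotherapy regimen is the only treatment difference between the cohorts. Section 4.2.3 defines the primary endpoint by DLT counts within each radiation dose cohort, so the label must mean the same thing throughout. Patients with locally advanced pancreatic cancer are restricted to 8 Gy x 3, that is, Cohort 1. Read by cohort number, Table 8 gives that cohort a single treatment day.

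**Working it through.** **Inputs**

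- Regimens: Cohort 1 is 8 Gy x 3 and Cohort 2 is 17 Gy x 1 (Sections 2.1, 5.2, 5.8 and 8).
- Treatment days by regimen: three 8 Gy fractions on Days 8, 10 and 12; one 17 Gy fraction on Day 8; each plus or minus 3 days (Section 7.1).
- Visit rule: last fraction + 30 days, plus or minus 7 (Table 8 and Section 7.1).
- DLT window: ends 35 days after the last fraction (Section 2.1).

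**Total dose = dose per fraction x number of fractions**

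- Cohort 1: 8 x 3 = 24 Gy.
- Cohort 2: 17 x 1 = 17 Gy.

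The printed 24 Gy over 3 fractions is reproduced only for Cohort 1. The two adjacent sentences in Section 5.2 therefore give Cohort 2 totals of 17 Gy and 24 Gy, which differ by 24 − 17 = 7 Gy.

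**Visit day = last fraction + 30**

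| | Cohort 1 | Cohort 2 |
|---|---|---|
| Nominal last fraction | Day 12 | Day 8 |
| Visit by the rule | 12 + 30 = Day 42 | 8 + 30 = Day 38 |
| Window by the rule | Days 35–49 | Days 31–45 |
| Printed visit (7.1) | Day 38 | Day 42 |
| Printed window | Days 31–45 | Days 35–49 |
| Printed visit, days after last fraction | 38 − 12 = 26 | 42 − 8 = 34 |
| Part of printed window outside the rule | Days 31–34 (19–22 days after) | Days 46–49 (38–41 days after) |

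Day 42 is reproduced only for Cohort 1 and Day 38 only for Cohort 2. The printed pair is an exact exchange, and it matches the exchange in the Table 8 header.

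**Effect of the 3-day treatment allowance**

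- Cohort 1, last fraction Day 9 to Day 15: the printed Day 38 is 38 − 9 = 29 to 38 − 15 = 23 days after it.
- Cohort 2, fraction Day 5 to Day 11: the printed Day 42 is 42 − 5 = 37 to 42 − 11 = 31 days after it.

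Both printed days stay within 23 to 37 days throughout. Only the edges of the printed windows can fall outside, and how much does so depends on the actual treatment day. For Cohort 1 finishing on Day 9, the rule gives Days 32–46, so only Day 31 is out. Finishing on Day 15, it gives Days 38–52, so Days 31–37 are out. For Cohort 2 treated on Day 11, the rule gives Days 34–48, so only Day 49 is out. Treated on Day 5, it gives Days 28–42, so Days 43–49 are out.

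**DLT window.** It is counted from each patient's actual last fraction, so its nominal end is 12 + 35 = Day 47 for Cohort 1 and 8 + 35 = Day 43 for Cohort 2, whatever the cohort is called.

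**The case against.** The best case on the other side is that this is a clerical slip with almost no consequence. The regimen is printed beside the cohort number in most places. The prescription is correct one sentence before the wrong total, and 24 Gy over 3 fractions is visibly 8 x 3. The visit days are a parenthesis derived from a rule stated in the same line, and both printed days satisfy that rule. Nothing in the safety decision or the analysis changes.

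Much of this stands. The Section 5.2 sentence mislabels one cohort and is not a full exchange; only Table 8 and the visit line swap both. The 7 Gy figure is a difference between nominal totals in different fractionations. Read literally, the sentence gives Cohort 2 the trial's other regimen and does not add 7 Gy to a single fraction. The effect on visit timing is small.

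It is not a reason to leave the text alone. A stated total dose and the flow chart's treatment days are instructions, and no reading reconciles them with Table 3. Section 5.2.1.2 rules out radiotherapy modification, so a dose-change provision cannot explain the 24 Gy. The Section 5.2 sentence and the visit line are running prose, so a broken table cannot explain those two either.

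**Conclusion.** The contradiction is real and should be fixed. Three current, operative places assign the wrong regimen or visit day to a cohort number. As printed, Cohort 2 has two different totals, 17 Gy and 24 Gy. With nominal treatment days, the post-radiotherapy visit falls 26 days (Cohort 1) or 34 days (Cohort 2) after the last fraction instead of 30, within the permitted 7 days.

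This rests on one assumption: that the mapping in Sections 2.1, 5.2, 5.8 and 8 is the intended one. The weight of the text supports it. There is no evidence in the documents that any patient was wrongly treated or classified, and none is alleged. The sample size, the DLT window, the DLT rule and the planned response analyses do not change.

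**What to change.** After the sponsor confirms the mapping, amend three places:

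1. **Section 5.2, dose paragraph:** state a total of 24 Gy in 3 fractions for Cohort 1 and 17 Gy in 1 fraction for Cohort 2.
2. **Table 8, radiotherapy header:** Cohort 1, Days 8, 10 and 12 ± 3; Cohort 2, Day 8 ± 3.
3. **Section 7.1, post-radiotherapy visit:** Day 42 ± 7 for Cohort 1 and Day 38 ± 7 for Cohort 2.

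The same amendment could deal with a separate, lesser point. One sentence in Section 4.2.2 still names 10.0 mg/kg every 2 weeks as the pembrolizumab dose for this trial, while Section 2.1, Table 2 and the infusion days give 200 mg every 3 weeks. That sentence should be brought into line. The surrounding rationale also discusses weight-based dosing and a 2-weekly schedule, so it needs a read-through as well.

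The cost is wording in three places, plus the rationale sentence, in a single amendment, with no change to the design or the analysis.

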5.2.1.1 Dose Selection

The rationale for selection of pembrolizumab and radiotherapy doses to be used in this trial is provided in Section 4.0 – Background and Rationale.

Details on the dose preparation and administration are provided in the Merck Protocol, reference.

5.2.1.2 Dose Modification

PEMBROLIZUMAB will be withheld for drug-related Grade 3 or 4 hematologic toxicities (with the caveats as shown in Table 4 below) or Grade 3 or 4 non-hematological toxicity including laboratory abnormalities, and severe or life-threatening AEs.

Table 4: Dose modification guidelines for drug-related adverse events.

Toxicity	Grade	Hold Treatment (Y/N)	Timing for restarting treatment	Dose/Schedule for restarting treatment	Discontinue Subject (after consultation with Sponsor)
Hematologic al Toxicity	1, 2	No	N/A	N/A	N/A
	3* *Excluding Grade 3 neutropenia, anemia, and thrombocytopenia	Yes	Toxicity resolves to Grade 0-1 or baseline	May increase the dosing interval by 1 week	Toxicity does not resolve within 12 weeks of last infusion Permanent discontinuation should be considered for any severe or life-threatening event
	4	Yes	Toxicity resolves to Grade 0-1 or baseline	May increase the dosing interval by 1 week	Permanent discontinuation should be considered for any severe or life-threatening event
Non-hematologica l toxicity Note: Exception to be treated similar to grade 1 toxicity • Grade 2 alopecia • Grade 2 fatigue	1	No	N/A	N/A	N/A
	2	Consider withholdin g for persistent symptoms	Toxicity resolves to Grade 0-1 or baseline	Clinical AE resolves within 4 weeks: Same dose and schedule (reference Section 5.6.1.2 for recommendations regarding pneumonitis) Clinical AE does not resolve within 4 weeks: May increase	Toxicity does not resolve within 12 weeks of last infusion

Toxicity	Grade	Hold Treatment (Y/N)	Timing for restarting treatment	Dose/Schedule for restarting treatment	Discontinue Subject (after consultation with Sponsor)
For additional information regarding Adverse Events with a potential Immune-Etiology reference Section 5.6.1.1.				the dosing interval by 1 week for each occurrence	
	3, 4	Yes	Toxicity resolves to Grade 0-1 or baseline	May increase the dosing interval by 1 week for each occurrence	Toxicity does not resolve within 12 weeks of last infusion Permanent discontinuation should be considered for any severe or life-threatening event

In case toxicity does not resolve to Grade 0-1 within 12 weeks after last infusion, trial treatment should be discontinued after consultation with the Sponsor. With investigator and Sponsor agreement, subjects with a laboratory adverse event still at Grade 2 after 12 weeks may continue treatment in the trial only if asymptomatic and controlled. For information on the management of adverse events, see Section 5.6.1.

Subjects who experience a recurrence of the same severe or life-threatening event at the same grade or greater with re-challenge of PEMBROLIZUMAB should be discontinued from trial treatment.

There will be no modification of radiotherapy.

5.2.2 Timing of Dose Administration

Trial treatment should be administered on Day 1 of each cycle after all procedures/assessments have been completed as detailed on the Trial Flow Chart (Section 6.0). Trial treatment may be administered up to 3 days before or after the scheduled Day 1 of each cycle due to administrative reasons.

All trial treatments will be administered on an outpatient basis.

PEMBROLIZUMAB will be administered as a 30 minute IV infusion (treatment cycle intervals may be increased due to toxicity as described in Section 5.2.1.2). Sites should make every effort to target infusion timing to be as close to 30 minutes as possible. However, given the variability of infusion pumps from site to site, a window of -5 minutes and +10 minutes is permitted (i.e., infusion time is 30 minutes: -5 min/+10 min).

The Procedures Manual contains specific instructions for PEMBROLIZUMAB dose calculation, reconstitution, preparation of the infusion fluid, and administration.

5.2.3 Trial Blinding/Masking

This is an open-label trial; therefore, the Sponsor, investigator and subject will know the treatment administered.

5.3 Stratification and Randomization

During the Safety Phase of this study, patients will be stratified on the basis of having received prior immunotherapy (see Table 3). During the Expansion Phase, patients will be stratified by disease site. If both fractionation regimens are safe, then we will randomize patients. Otherwise, all patients will be enrolled on the single regimen determined to be safe. Randomization will aid in the preliminary assessment of clinical response by avoiding selection bias. The randomization procedure is described in the Statistical Section.

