2.0 TRIAL DESIGN

2.1 Trial Design

This is a Phase I cohort study of a fixed dose of Pembrolizumab in combination with two distinct regimens of hypofractionated radiotherapy. There will be five groups of patient diagnoses:

- Metastatic melanoma patients who have progressed while on PD-1 or PDL-1 therapy
- Metastatic NSCLC patients who have progressed while on PD-1 or PDL-1 therapy
- Metastatic & locally advanced pancreatic cancer patients
- Metastatic Breast cancer patients
- Other metastatic cancer patients

Pembrolizumab will be administered at a dose of 200 mg every 3 weeks beginning 7 days (+/- 3 days) prior to the first fraction of hypofractionated radiation and will continue for a total of 6 cycles. In the initial **Safety Phase**, there will be two cohorts of patients based upon the radiotherapy dose delivered to the index metastatic lesion in the lung, liver, bone or soft tissue:

Cohort 1: 8 Gy x 3 to the index lesion

[figure not shown]
Cohort 2: 17 Gy x 1 to the index lesion*

*Subjects with locally advanced pancreatic cancer will be enrolled only in the 8 Gy x 3 cohort.

Patients are stratified by prior PD-1 therapy. 24 patients will be enrolled, 12 per stratum and 6 per fractionation cohort. Standard safety decision-making will be used. The regimen is safe if 0-1 dose-limiting toxicities (DLT) in 6 patients (3 from each strata). Enrollment in a cohort will stop if 2+ DLT are observed within a cohort at any time during the safety phase. If 2+ DLT are observed in Cohort 1, then Cohort 2 will still be tested. Cohort 1 → Cohort 2 is **not** an escalation of dose. DLT is defined as any Grade 3 or higher non-hematological toxicity and any Grade 4 hematological toxicity that is probably, possibly or definitely related to the combination of Pembrolizumab and hypofractionated radiotherapy. The window in which DLTs will be recorded is from the first Pembrolizumab infusion to 35 days after the last radiation fraction.

In the **Expansion Phase**, patients will be stratified by disease site. If both fractionation regimens are safe, then we randomize patients. Otherwise, all patients will be enrolled on the single regimen determined to be safe. 46 patients will be enrolled. Randomization will aid in the preliminary assessment of clinical response by avoiding selection bias. Accrual is expected to occur over 24 months or 3-4 subjects per month.

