5.9 Clinical Criteria for Early Trial Termination

Early trial termination will be the result of the criteria specified below:

1. Quality or quantity of data recording is inaccurate or incomplete
2. Poor adherence to protocol and regulatory requirements
3. Incidence or severity of adverse drug reaction in this or other studies indicates a potential health hazard to subjects
4. Plans to modify or discontinue the development of the study drug

In the event of Merck decision to no longer supply study drug, ample notification will be provided so that appropriate adjustments to subject treatment can be made.

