8.0 STATISTICAL ANALYSIS PLAN

This is a stratified phase I trial with 2 phases: a safety phase and an expansion phase.

Safety Phase: Pembrolizumab is fixed. Two radiotherapy fractionation schedules are tested: 8 Gy x 3 and 17 Gy x 1. Patients are stratified by prior PD-1 therapy. 24 patients will be enrolled, 12 per stratum and 6 per fractionation cohort.

Table 11

	Progressed on Prior PD-1 (Melanoma or NSCLC)	Cohort 1: 8 Gy x 3 Number of Patients	Cohort 2: 17 Gy x 1 Number of Patients	TOTAL
		6	6	

May 3, 2017

Confidential  Limited Access

Stratify	No Prior PD-1 (Pancreas, Breast or Other cancers)	6	6*	12
	TOTAL	12	12	24
	* Breast or Other cancer patients only			

Safety Phase Decision-making: Dose limiting toxicity (DLT) is defined in Sections 2.1 and 5.2. The regimen is considered safe if 0-1 DLTs are observed in 6 patients within a stratum. Stop if 2+ DLT at any time. If 2+ DLT in Cohort 1, then Cohort 2 will still be tested. Cohort 1 → Cohort 2 is not an escalation of dose.

Expansion Phase: Patients are now stratified by disease site.

- If both fractionation regimens are considered safe for both prior PD-1 therapy strata, then we will randomize patients. Randomization will aid in our preliminary assessment of clinical response by avoiding selection bias. Although unlikely, if only one of the fractionation regimens is considered safe for both prior PD-1 therapy strata, then all patients will be enrolled on the fractionation regimen which was determined to be safe.

Table 12

Disease	Randomize		Number of Randomized Patients
	Cohort 1: 8 Gy x 3 Number of Patients	Cohort 2: 17 Gy x 1 Number of Patients	
Melanoma	7	7	14
NSCLC	7	7	14
Pancreas	6	0	6*
Breast	3	3	6
Other cancers	3	3	6
TOTAL	26	20	46
	* Pancreas patients are not randomized, they are assigned to 8 Gy x 3		

Expansion Phase Decision-making: We will first evaluate response rate by fractionation cohort. We will pool all disease sites. This is a global assessment of RADVAX™ by fractionation cohort. Of 38 patients in cohort 1, 26 (68%) and of 32 patients in cohort 2, 20 (63%) will have been randomized to treatment in the expansion phase, which strengthens any comparative conclusions, although preliminary. Immune PD markers will also be examined by fractionation cohort.

Table 13

	Cohort 1: 8 Gy x 3 Number of Patients	Cohort 2: 17 Gy x 1 Number of Patients	STUDY TOTAL
Safety phase	12	12	24
Expansion phase	26	20	46
TOTAL	38	32	70

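### The decision rule that follows the Safety Phase differs between Sections 2.1, 5.2/5.3 and 8, and no version gives an action for every outcome

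*Combined protocol and SAP*

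**What the plan says.** **Structure.** Section 5.2: "24 patients will be enrolled, 12 per stratum and 6 per fractionation cohort within each stratum".

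**Definition of a safe regimen.** There are three versions.
- Section 2.1 pools the strata: "The regimen is safe if 0-1 dose-limiting toxicities (DLT) in 6 patients (3 from each strata"). Section 4.2.3, on the primary endpoint, also counts DLTs per radiation cohort and does not mention strata.
- Section 5.2 separates them: "The regimen is safe if no more than 0-1 dose-limiting toxicities (DLT) are observed in 6 patients within a cohort within a stratum".
- Section 8 defines safety by stratum, "The regimen is considered safe if 0-1 DLTs are observed in 6 patients within a stratum", but its actions need a regimen to be safe in both strata.

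**Action afterwards.** Sections 2.1, 5.2 and 5.3 give two branches with no stratum condition: randomise if both regimens are safe; if not, "Otherwise, all patients will be enrolled on the single regimen determined to be safe". Section 8 randomises if both regimens are safe in both strata, and uses a single regimen "if only one of the fractionation regimens is considered safe for both prior PD-1 therapy strata". It calls the second outcome unlikely.

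**Gate and stops.** Section 5.2 opens expansion for a stratum once 12 of its patients have been treated and the DLT observation time has passed. It names no pass condition. The stopping rule is tied to the Safety Phase: "Enrollment in a cohort within a stratum will stop if 2+ DLT are observed within that cohort at any time during the safety phase". Section 5.9 opens with "Early trial termination will be the result of the criteria specified below" and lists four criteria. The nearest, item 3, is a general adverse-reaction hazard.

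**The concern.** The rule acts on the trial's primary endpoint, and it decides which patients among the 46 in the Expansion Phase receive which regimen. A regimen can pass in one stratum and fail in the other, yet no section says what happens to the two strata in that case. Nor does any section say what happens if no regimen qualifies. Staff would have to choose between sections after seeing the DLT data. Depending on the section chosen, the trial could have no instruction, could close a stratum in which a regimen passed, or could assign a disease group to a regimen that met the stopping boundary in that group's own stratum.

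**Working it through.** **The plan's own figures.** 2 strata × 2 regimens × 6 = 24, and 14 + 14 + 6 + 6 + 6 = 46, for a total of 70. All three reproduce. The pooled wording of Section 2.1 would need only 2 × 6 = 12 patients, so the 24 fits the within-stratum structure.

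**Counting outcomes.** Four cells, each pass or fail, give 2⁴ = 16 patterns. Section 8 covers both regimens passing in both strata (1 pattern) and exactly one regimen passing in both (6 patterns). That leaves 16 − 7 = 9:

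| Pattern | Count | Section 8 | Within-stratum definition with Section 5.3 wording |
|---|---|---|---|
| All four cells fail | 1 | No action | No action |
| One cell passes | 4 | No action | All patients on that regimen, including the stratum where it failed |
| Crossed: each regimen passes in a different stratum | 2 | No action | Both regimens safe somewhere, so randomise; one arm in each stratum has failed there |
| Both regimens pass in the same single stratum | 2 | No action | Both regimens safe somewhere, so randomise; both arms in the other stratum have failed there |

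Under the pooled rule in Section 2.1 there are four outcomes and no stratum-specific failure, but the outcome in which neither regimen is safe has no action.

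**Probabilities.** The documents state no DLT rate. Assumption: the same true rate p in all four cells, with independent cells.
- One cell passes with probability q = (1−p)⁶ + 6p(1−p)⁵.
- No regimen passes in both strata: (1−q²)².
- Neither regimen is safe under the pooled rule, 6 patients per regimen: (1−q)².

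| p | q | No regimen passes both strata | Pooled: neither safe |
|---|---|---|---|
| 5% | 0.967 | 0.4% | 0.1% |
| 10% | 0.886 | 4.6% | 1.3% |
| 15% | 0.776 | 15.8% | 5.0% |
| 20% | 0.655 | 32.5% | 11.9% |
| 25% | 0.534 | 51.1% | 21.7% |

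Split of the 32.5% at p = 20% (unrounded q = 0.65536):
- all four fail, (1−q)⁴ = 1.4%
- one cell passes, 4q(1−q)³ = 10.7%
- crossed, 2[q(1−q)]² = 10.2%
- both regimens pass in one stratum only, 2[q(1−q)]² = 10.2%

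The mixed results therefore make up 32.5 − 1.4 = 31.1 points. At p = 10% the same four terms are 0.02%, 0.5%, 2.0% and 2.0%.

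If the strata differ, with rates of 10% and 30% (q = 0.886 and 0.420), the chance that no regimen passes both is (1 − 0.886 × 0.420)² = 39.4%.

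**Does another passage close the gap?** The Section 5.2 gate works stratum by stratum, so one stratum can open before the other has a result. Section 8's both-strata condition cannot be evaluated at that moment. Section 5.2 also says that completing the prior-PD-1 stratum opens Pancreas, Breast and Other. This looks like a slip, but it loosens the link between a disease group and its own stratum.

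**The case against.** A reader might infer that the plan directs enrolment on a failed regimen in all nine patterns. The documents do not support that. Under Section 8 no regimen qualifies in those patterns, so the text is silent and assigns nobody. The adverse assignment arises only from the within-stratum definition combined with the Section 5.3 wording, and on that reading eight of the nine patterns do have an action. Missing action and wrong assignment therefore belong to different readings and should not be added together. Section 5.3 can fairly be called a summary, with Section 8 as the fuller rule.

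Other limits also stand in part. The 2+ DLT rule stops a cell, and nothing expressly reopens it; but the Section 5.2 stop is worded for the Safety Phase and does not govern assignment in expansion. A cell stopped early could keep its stratum below 12 treated patients. That barrier is partial and accidental: it fails if the second DLT appears after the cell has filled, and it would equally block the single-regimen branch that the plan does intend.

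A reader might also infer that Section 5.9 leaves no ground for stopping. That is too strong. Item 3 could cover repeated related DLTs, and grade 3 or higher events go to the DSMC within 5 days. But item 3 is discretionary and is not tied to the DLT rule, a stratum or a regimen. Section 5.9 also concerns ending the whole trial, and eight of the nine patterns contain a passing cell.

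Finally, if true DLT rates are near 5% the open outcomes are rare (0.4%).

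**Conclusion.** The point holds as a conflict between sections and an incomplete rule. The definition of a safe regimen differs between Sections 2.1, 5.2 and 8, and every version leaves at least one outcome without an action: nine of 16 under Section 8, the all-fail pattern under the within-stratum definition with Section 5.3, and neither regimen safe under the pooled rule. Placement of a disease group on a regimen that failed in its own stratum is possible on one literal reading and is not required by the plan as a whole.

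The pattern counts rest on the text alone. The probabilities rest on assumed, equal and independent DLT rates. They run from 0.4% at a 5% rate to 51.1% at 25%, and show that the gap is small only if DLTs are uncommon.

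**What to change.** Reconcile Sections 2.1, 5.2, 5.3, 5.9 and 8 as follows:
- Use one definition of a safe regimen throughout: pooled, within stratum, or safe in both strata.
- Make the gate to the Expansion Phase depend on that result as well as on numbers treated and elapsed time, and correct the sentence on which disease groups the prior-PD-1 stratum opens.
- State an action for every Safety Phase outcome, including no regimen qualifying and results that differ by stratum, and make Section 5.9 consistent with it.
- State the 46-patient expansion and Table 12 as conditional on the safety results.
- Report DLT results by regimen within stratum.

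Which clinical rule to adopt is for the sponsor and investigator. The cost is a few sentences of protocol and SAP wording. The drawback is that the expansion numbers can no longer be presented as fixed.
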